2.3. Benefit/Risk Assessment

C difficile is the main cause of nosocomial infectious diarrhea in industrialized countries.^{2,3,4,5,6} It accounts for 20% to 30% of cases of antibiotic-associated diarrhea and is the most commonly recognized cause of infectious diarrhea in healthcare settings.⁷ To date, there is no approved vaccine to prevent primary or recurrent CDI. The increasing burden of CDI on patients and on the healthcare system demonstrates that prevention of CDI constitutes a significant unmet medical need.

The B5091001 first-in-human study, which assessed 3 antigen dose levels (50, 100, and 200 µg) administered either alone or in combination with AlOH at Months 0, 1, and 6 to healthy adults 50 to 85 years of age, demonstrated that the *C difficile* vaccine formulations and dose levels administered were generally well tolerated. Local reactions and systemic events were predominantly mild to moderate, and comprised mostly injection site pain, headache, and fatigue. There was little difference in the number of participants reporting AEs between the dose groups and the placebo group or between vaccine formulations.

The B5091009 Phase 2 study, which assessed 2 antigen dose levels (100 and 200 µg) administered in combination with AlOH at Months 0, 1, and 6 or Days 1, 8, and 30 to healthy adults 65 to 85 years of age, demonstrated that both regimens and both dose levels administered were generally well tolerated. Local reactions were predominantly mild to moderate, with injection site pain being the most frequent manifestation. After Dose 2, local reactogenicity was greater when the vaccine was administered at Day 8 compared to Month 1, particularly for the 200-µg dose level. Systemic events were also predominantly mild to moderate and the incidences of individual events were similar between the placebo group, the 100-µg dose group, and the 200-µg dose group. Within each regimen, the overall AE incidence rates were also similar between the placebo, 100-µg, and 200-µg dose groups. For both regimens, SAEs were numerically higher in the 100-µg and 200-µg dose groups than in the placebo group. However, there was no pattern to these events and no safety concern was identified.

Both studied dose levels resulted in substantial neutralizing antitoxin A and B titers, with the immunogenicity profile following 3 doses administered at Months 0, 1, and 6 being preferred. In addition, the 200-µg dose level was more immunogenic than the 100-µg dose level.

Study B5091010, a first-in-Japanese participants study, was a Phase 1, placebo-controlled, randomized, observer-blinded study to assess the safety, tolerability (primary objectives), and immunogenicity (secondary objectives) of 2 antigen dose levels in 2 different dosing regimens (Months 0, 1, and 6 month regimen] or Days 1, 8, and 30 [day regimen]) in healthy Japanese adults, 65 to 85 years of age. The C difficile vaccine was well tolerated when administered in the 0-, 1-, and 6-month regimen with no unexpected AEs observed in this regimen, indicating a favorable safety profile in this elderly population of healthy Japanese adults 65 to 85 years of age when administered in the month regimen. There were 3 participants in the day regimen who reported severe local reactions, leading to the triggering of a stopping rule and discontinuation of subsequent enrollment and dosing in the day regimen; these local reactions resolved. The proportion of participants reporting local reactions and systemic events was generally low across all vaccine groups in the month regimen. In both the month and day regimens, most events were of mild to moderate severity. There were no notable differences between the 100- or 200-ug dose groups observed within each regimen based on an evaluation of the proportion of participants reporting AEs, SAEs, or newly diagnosed chronic medical conditions (NDCMCs).

Thus, *C difficile* vaccinations at a dose of 100 or 200 µg were generally well tolerated when given according to a Month 0, 1, and 6 regimen.

Pfizer considers that the available information from Studies B5091001, B5091009, and B5091010 with PF-06425090 supports a favorable benefit-risk profile for studies administrating 3 doses of the *C difficile* vaccine at dose levels up to 200 µg as a potential prevention against CDI. It is expected that this would also apply to a 2-dose regimen of the vaccine given 6 months apart, and especially so since the reactogenicity after Dose 2 (at Month 1 seen in all 3 studies, B5091001, B5091009, and B5091010) was the most pronounced. In addition, this is further supported by review of safety data from the B5091007 and B5091008 studies

has not identified a safety concern.

More detailed information about the known and expected benefits and risks and reasonably expected AEs of *C difficile* vaccine may be found in the investigator's brochure (IB), which is the single reference safety document (SRSD) for this study.

3. OBJECTIVES, ESTIMANDS, AND ENDPOINTS

Objectives	Estimands	Endpoints		
Primary Immunogenicity:	Coprimary Immunogenicity:	Primary Immunogenicity:		
To demonstrate the noninferiority of a 2-dose regimen of the C difficile vaccine compared to a 3-dose regimen of the C difficile vaccine.	• For each of toxin A– and toxin B–specific neutralizing antibody levels: Adjusted GMC ratio, estimated by the ratio of the adjusted GMC (adjusted for baseline concentration) for the 2-dose regimen to the adjusted GMC for the 3-dose regimen, in participants receiving C difficile vaccine and in compliance with the key protocol criteria (evaluable participants).	C difficile toxin A- and toxin B-specific neutralizing antibody levels at Month 7 in each regimen.		
	• For each of toxin A– and toxin B–specific neutralizing antibody levels: Seroresponse difference, estimated by the difference between the 2-dose regimen and the 3-dose regimen in the percentage of participants achieving seroresponse, in participants receiving C difficile vaccine and in compliance with the key protocol criteria (evaluable participants).			
	Seroresponse for each of toxin A– and toxin B– specific neutralizing antibody levels: For both seronegative (baseline concentration < LLOQ) and seropositive (baseline concentration ≥ LLOQ) participants, seroresponse is achieved for a specific participant if that participant has at least a 4-fold rise from the baseline neutralizing antibody level following vaccination.			
Primary Safety:	Primary Safety:	Primary Safety:		
• To evaluate the safety of C difficile vaccine when administered to participants in a 2-dose regimen or a 3-dose regimen by assessing local reactions and systemic events, AEs, and SAEs.	 In participants receiving at least 1 dose of investigational product, the incidence rate estimated by the percentage of participants reporting local reactions. In participants receiving at least 1 dose of investigational product, the incidence rate estimated by the percentage of 	 Local reactions (pain, erythema, and induration), as self-reported on e-diaries for up to 7 days following each dose of investigational product in each regimen. Systemic events (fever, vomiting, headache, fatigue, new or worsening muscle pain, and new or worsening joint 		

PFIZER CONFIDENTIAL

Objectives	Estimands	Endpoints
	participants reporting systemic events. In participants receiving at least 1 dose of investigational product, the incidence rate estimated by the percentage of participants reporting nonserious AEs. In participants receiving at least 1 dose of investigational product, the incidence rate estimated by the percentage of participants reporting SAEs.	 pain), as self-reported on ediaries for up to 7 days following each dose of investigational product in each regimen. Nonserious AEs from signing of the ICD to 1 month after receipt of the last dose of investigational product in each regimen. SAEs from signing of the ICD to 6 months after receipt of the last dose of investigational product in each regimen.
Secondary:	Secondary:	Secondary:
To demonstrate the noninferiority of a 2-dose regimen of the C difficile vaccine compared to a 3-dose regimen of the C difficile vaccine. a	 For each of toxin A– and toxin B–specific neutralizing antibody levels: Adjusted GMC ratio, estimated by the ratio of the adjusted GMC (adjusted for baseline concentration) for the 2-dose regimen to the adjusted GMC for the 3-dose regimen, in participants receiving C difficile vaccine and in compliance with the key protocol criteria (evaluable participants). For each of toxin A– and toxin B–specific neutralizing antibody levels: Seroresponse difference, estimated by the difference between the 2-dose regimen and the 3-dose regimen in the percentage of participants achieving seroresponse, in participants receiving C difficile vaccine and in compliance with the key protocol criteria (evaluable participants). Seroresponse for each of toxin A– and toxin B– specific neutralizing antibody levels: For both seronegative (baseline concentration < LLOQ) and seropositive (baseline concentration ≥ LLOQ) participants, seroresponse is 	C difficile toxin A— and toxin B—specific neutralizing antibody levels at Month 12 in each regimen. Output Description:

	Objectives	Estimands	Endpoints
		the baseline neutralizing antibody level following vaccination.	
CCI			

a. Noninferiority (NI) analysis for Month 12 will be performed only after the NI criteria are met in terms of the GMC ratio and the seroresponse difference at Month 7.

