4. STUDY DESIGN

4.1. Overall Design

This is a Phase 3, randomized, observer-blinded study to evaluate the immunogenicity, safety, and tolerability of a 2-dose *C difficile* vaccine regimen compared to a 3-dose *C difficile* vaccine regimen in adults 50 years of age and older.

Participants will be randomly assigned in parallel in a 1:1 ratio to receive one of the following dosing regimens according to the visit schedule:

- 2-Dose: Participants will receive 1 dose of *C difficile* vaccine (200 µg total toxoid per dose) at Visit 1 (Month 0) and Visit 4 (Month 6) and 1 dose of placebo (0.9% sodium chloride or normal saline) at Visit 2 (Month 1).
- 3-Dose: Participants will receive 1 dose of *C difficile* vaccine (200 µg total toxoid per dose) at Visit 1 (Month 0), Visit 2 (Month 1), and Visit 4 (Month 6).

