- Ask the participant to contact the site staff or investigator immediately if any significant illness or hospitalization occurs.

- Schedule a telephone call for the next study visit.
- Complete the source documents.
- Complete the CRF.

Visit 3: Month 2 - Telephone Contact (28 to 42 Days After Visit 2)

- Contact the participant by telephone to determine whether any AEs or SAEs have occurred since the last study visit. Record and report findings as described in Section 8.3 and the SoA. Review AEs that were ongoing from the previous visit and record their stop dates or confirm if they are still continuing.
- Follow up on any ongoing local reactions or systemic events.
- Record nonstudy vaccines as described in Section 6.5.
- Discuss contraceptive use.
- Ensure that the participant continues to be eligible for the study and does not meet any of the withdrawal criteria as described in Section 7.2.
- Ask the participant to contact the site staff or investigator immediately if any significant illness or hospitalization occurs.
- Schedule an appointment for the participant to return for the next study visit.
- Complete the source documents.
- Complete the CRF.

Visit 4: Month 6 - Vaccination 3 (140 to 168 Days After Visit 2)

- Review the participant's e-diary data and follow up on any ongoing local reactions or systemic events.
- Ensure that the participant continues to be eligible for the study and does not meet any of the withdrawal criteria as described in Section 7.2.
- Based on clinical evaluation, determine whether any AEs or SAEs have occurred
 since the last study visit. Record and report findings as described in Section 8.3 and
 the SoA. Review AEs that were ongoing from the previous visit and record their stop
 dates or confirm if they are still continuing.
- Record nonstudy vaccines as described in Section 6.5.

- Collect a blood sample of approximately 20 mL for immunogenicity testing (Section 8.1.1).
- Measure and record the participant's oral temperature.
- For WOCBP, perform a urine pregnancy test and ensure the result is negative prior to vaccination (Section 8.2.4).
- Discuss contraceptive use.
- Ensure that none of the temporary delay criteria are met (Section 5.2.1).
- An appropriate site staff member (may be blinded or unblinded) will use the IRT system to obtain the participant's investigational product blinded carton number.
- Unblinded site staff will prepare and administer investigational product.

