3.5. Safety Endpoints

3.5.1. Adverse Events

Safety endpoints will include Pfizer standard safety endpoints collected in the study. An AE is defined as any untoward medical occurrence and can therefore be any unfavorable and unintended sign (including an abnormal laboratory finding), symptom, or disease (new or exacerbated) temporally associated with the use of study intervention, whether or not considered related to the study intervention.

The time period for actively eliciting and collecting AEs and SAEs for each participant begins from the time the participant provides informed consent through and including Visit 5 (Month 7) for AEs and through and including Visit 7 (Month 12) for SAEs. In addition, any AE occurring up to 48 hours after each blood draw, ie, after Visit 6 (Month 9) and Visit 7 (Month 12), will be recorded on the CRF. For participants who are screen failures, the active collection period ends when screen failure status is determined.

Overall AEs by category (any AE, related AEs, severe AEs, SAEs, etc) will be summarized by vaccine regimen from the date of the first dose through 1 month after the last dose (ie, including Visit 5 [Month 7]) for AEs and through 6 months after the last dose (ie, including Visit 7 [Month 12]) for SAEs. AEs and SAEs will be summarized by vaccine regimen from the date of the first dose through and including Visit 5 (Month 7) for AEs and through and including Visit 7 (Month 12) for SAEs, by MedDRA term. In addition, a participant-level listing of all AEs reported from the signing of the ICD through the day before the date of vaccination will also be provided. In general, all summaries will present the number and percentage of participants experiencing at least 1 event and the number of events for each regimen, and the exact 2-sided 95% CIs calculated using the Clopper-Pearson method.

A 3-tier approach will also be used to summarize AEs. Under this approach, AEs are classified into 1 of 3 tiers. For Tier 1 and Tier 2 AEs, the difference in the percentages and the 95% CI for the difference between vaccine regimens calculated using the test statistic proposed by Miettinen and Nurminen (1985)¹ will be provided. In addition, the p-value by the Miettinen and Nurminen method will be provided for Tier 1 events.

Tier 1 events: These are prespecified events of clinical importance and, if any, are maintained in a list in the product's Safety Review Plan.

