4.3. Safety Analysis Population

The safety analysis population (SAF) will include all participants who have received at least 1 dose of the investigational product. For reactogenicity analyses by dose, participants who received a different investigational product regimen from the regimen they were assigned will be included in the safety population for the summaries of individual vaccinations up until the point their regimen differs from the assigned regimen, at which point they would no longer be included. For AE analysis, such participants will be included in the AE summary in the group according to the second vaccine dose received.

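### Unsolicited AEs are compared between regimens only over one pooled window of about seven months; a supplementary Visit 2 to Visit 3 comparison would be far more precise on the one injection that differs

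*Protocol*

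**What the plan says.** Protocol section 4.1 gives both arms vaccine at Visits 1 and 4. They part only at Visit 2, where the 3-dose arm has vaccine and the 2-dose arm has "1 dose of placebo (0.9% sodium chloride or normal saline) at Visit 2 (Month 1").

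For unsolicited events, Protocol section 3 sets one endpoint window: "Nonserious AEs from signing of the ICD to 1 month after receipt of the last dose of investigational product in each regimen". SAP 3.5.1 starts the clock at the first dose instead and otherwise keeps a single interval: "AEs and SAEs will be summarized by vaccine regimen from the date of the first dose through and including Visit 5 (Month 7) for AEs". SAP 6.1.2.2 repeats that window for the primary safety analysis. SAP 3.5.1 plans a comparison between regimens at Tier level: "For Tier 1 and Tier 2 AEs, the difference in the percentages and the 95% CI for the difference between vaccine regimens". No post-dose interval is attached to it. The other AE summaries carry per-arm intervals, "the exact 2-sided 95% CIs calculated using the Clopper-Pearson method".

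Solicited reactions are handled differently. Protocol 9.4.2.1 and SAP 3.5.2 and 6.1.2.1 summarise them by regimen after each vaccination, with Visits 1, 2 and 4 as separate time points. Protocol 8.2.1 says that e-diary data need not also be entered as AEs.

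AEs are elicited at Visits 2 and 5, and the Visit 3 instruction in Protocol section 8 reads: "Contact the participant by telephone to determine whether any AEs or SAEs have occurred since the last study visit".

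**The concern.** The study exists to compare two doses with three, and nonserious AEs are a primary safety endpoint. The only treatment contrast is the Month 1 injection, and Protocol 2.3 reports that reactogenicity was most pronounced after that dose in three earlier studies. Yet no visible AE table isolates the period after it.

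The pooled window also takes in the weeks before Visit 2, when treatment is identical, and the long stretch between Visits 3 and 4, when no injection is recent. Background events there add noise to the comparison. Participants are selected for frequent healthcare contact or recent antibiotic use (Protocol 5.1), so a substantial background is plausible. A wide interval around a small pooled difference could then be read as evidence that the Month 1 dose adds no AEs, when the analysis had little chance of showing that it did.

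**Working it through.** **The plan's own figure.** Protocol 9.2: 1568 evaluable / (1 - 0.20) = 1960 randomised, so 980 per arm. This reproduces. The documents state no safety hypothesis, margin, power or expected AE rate, so there is no safety figure to reproduce.

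**Window lengths**, from the Schedule of Activities (Visit 2 is 28-42 days after Visit 1; Visit 3 is 28-42 and Visit 4 is 140-168 days after Visit 2; Visit 5 is 28-42 days after Visit 4):
- Visit 1 to Visit 5: 28 + 140 + 28 = 196 to 42 + 168 + 42 = 252 days.
- Before Visit 2 (identical treatment): 28/(28 + 168 + 42) = 12% to 42/(42 + 140 + 28) = 20% of the window.
- Visit 3 to Visit 4: 140 - 42 = 98 to 168 - 28 = 140 days.
- Months after Visits 2 and 4 together: (28 + 28)/(42 + 168 + 28) = 24% to (42 + 42)/(28 + 140 + 42) = 40%.

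**Any-AE illustration.** Assumptions: n = 960 dosed per arm; background any-AE risk q per month; seven independent months; excess of 4 percentage points in the month after Visit 2 and none elsewhere.
- Interval: p0 = q, p1 = q + 0.04.
- Pooled: p0 = 1 - (1 - q)^7, p1 = 1 - (1 - q)^6 (1 - q - 0.04). The difference is 0.04 (1 - q)^6.
- SE = sqrt[p0(1 - p0)/n + p1(1 - p1)/n]; power = Φ(difference/SE - 1.96).

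For q = 5%, interval: SE = sqrt[(0.0475 + 0.0819)/960] = 0.0116, power = Φ(3.45 - 1.96) = 93%. Pooled: p0 = 0.302, p1 = 0.331, SE = 0.0212, power = Φ(1.39 - 1.96) = 28%.

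| q per month | Visit 2-3: difference ± 95% half-width | Power | Pooled: difference ± half-width | Power |
|---|---|---|---|---|
| 5% | 4.0 ± 2.3 | 93% | 2.9 ± 4.2 | 28% |
| 8% | 4.0 ± 2.7 | 83% | 2.4 ± 4.5 | 19% |
| 10% | 4.0 ± 2.9 | 77% | 2.1 ± 4.5 | 15% |

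The pooled difference keeps (0.90)^6 = 53% to (0.95)^6 = 74% of the true excess, while the half-width grows by a factor of about 1.5 to 1.8.

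**Single terms.** Assumptions: n = 980 per arm; seven-month background B; the Month 1 vaccine dose adds an independent 2% chance of the event. At the midpoints of the visit windows the interval is 35 of 224 days, so its background is w = 1 - (1 - B)^(35/224). The pooled difference is (1 - B) × 0.02 and the interval difference is (1 - w) × 0.02.
- B = 2%: 1.96 versus 1.99 points; power 72% pooled, 97% in the interval.
- B = 5%: 1.90 versus 1.98 points; power 43% pooled, 91% in the interval.

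At term level the estimate hardly moves. What is lost is precision.

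**Starting the pooled comparison at Visit 2 instead.** Same any-AE model with six months in place of seven: power is 33% (q = 5%) or 18% (q = 10%), against 28% and 15%. Removing the identical-treatment weeks alone therefore achieves little.

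**The case against.** The strongest reply is that tolerability is already well served. The reactions that the protocol expects to be worst after Dose 2 are primary safety endpoints, reported by regimen after each vaccination, and kept largely out of the AE data. That stands, and it confines the point to unsolicited AEs. It does not close the gap: the e-diary covers 7 days and a fixed symptom list, so anything else appears only in the pooled AE tables.

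Three stronger readings are tempting, and the documents support none of them.
- A reader might infer that a real difference would be largely diluted away. It would not: 53-74% of an any-AE excess survives in the illustration, and over 95% for terms with a background of 5% or less.
- A reader might blame the shared treatment before Visit 2. That period is only 12-20% of the window. The long gap between Visits 3 and 4 contributes more.
- A reader might take SAP 4.3 as conceding that the second dose is where AE contrast lies, since it has participants "included in the AE summary in the group according to the second vaccine dose received". That rule applies only to participants who received a regimen other than the one assigned.

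It is also fair to say that a whole-regimen window is a legitimate endpoint; that SAP 6.6.1 describes safety analysis as hypothesis-generating; and that related and severe AEs are summarised by regimen, which may reduce background noise. These are reasons to keep the pooled analysis, not reasons to omit a sharper supplement. Finally, parts of both documents are redacted, so a per-dose AE summary there cannot be excluded. The visible AE sections contain none.

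**Conclusion.** The point holds as a limited, inexpensive improvement. The visible plan compares unsolicited AEs between regimens only over 196-252 days, although the arms differ in one injection. The cost is mainly precision: under the stated assumptions, power of 15-28% pooled against 77-93% for the Visit 2 to Visit 3 interval. The direction does not depend on the exact rates, but the size does. The background risk, the 4-point excess, independence between months and the absence of any excess after Visit 4 are all assumptions.

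The documents do not support a conclusion that the primary safety endpoint is wrongly defined, or that the trial cannot see a tolerability difference at Month 1. What the pooled analysis cannot do well is support a statement about unsolicited AEs attributable to the Month 1 dose.

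**What to change.** Keep the primary endpoint and the pooled Tier 1 and Tier 2 analysis as they are, including the start at first dose. Add to SAP 3.5.1 and 6.1.2.2 a supplementary summary of nonserious AEs (any AE, and Tier 1 and Tier 2 terms) with onset from the Visit 2 dose to Visit 3, among participants dosed at Visit 2, with the Miettinen-Nurminen difference and 95% CI. Receipt of an injection at Visit 2 is settled before the arms differ, so this denominator should not favour either arm.

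If a Visit 4 to Visit 5 table is also wanted, make it descriptive and say that receiving the Visit 4 dose is decided after the arms diverge. Withdrawals, or vaccination stopped after a confirmed related Grade 4 reaction, could remove participants unevenly.

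The cost is SAP wording and a few tables from data already collected, with no new visits. The downside is more descriptive comparisons without multiplicity control, which the SAP should state.
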